Heavy Episodic Drinking and Sleep Difficulties. Research demonstrates bidirectional causal links between alcohol misuse and sleep difficulties. Alcohol interferes with sleep quality and exacerbates daytime sleepiness (Roehrs & Roth, 2001; [name], 1997). Despite initial reductions in time to fall asleep (sleep onset latency; SOL) associated with alcohol use, tolerance to this effect accrues rapidly, which can lead to increased doses of alcohol in an attempt to promote sleep. Alcohol use also results in fragmented sleep, particularly in the second half of the sleep cycle due to suppression of REM sleep (and related REM rebound in subsequent nights) (Hershner & Chervin, 2014; Lund et al., 2010; Roehrs & Roth, 2001; [name], 1997). Alcohol withdrawal is associated with sleep impairment, making sleep difficulties a risk for relapse among those attempting to abstain ([name], 1997). However, alcohol's impact on sleep is not limited to those with alcohol use disorders; among adolescents the prevalence of sleep disturbance is higher in those who use alcohol than those who do not (Morioka et al., 2013). There is a strong relationship between HED and sleep difficulties among adolescents and YA which increases in magnitude with frequency of HED (Popovici & French, 2013). Almost 12% of YA who consume alcohol also use alcohol as a sleep aid ([name] & Bramoweth, 2010) and among students who report HED, those with poorer sleep quality also report more alcohol consequences than those with better sleep (Kenney et al., 2012). Of note, sleep-deprived individuals are at greater risk for vehicular accidents with even modest doses of alcohol (Vakulin et al., 2007). Sleep deprivation can be acute (e.g., pulling an all-nighter) or chronically getting insufficient amount or quality of sleep (Hershner & Chervin, 2014). Challenges relevant to YA include varying class or work schedules, leading to inconsistent sleep- and wake-times, and also late-night events (Hershner & Chervin, 2014), which can exacerbate poor sleep symptoms.

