4) Experience with assessment of and interventions for sleep difficulties. [name] is a national leader in sleep research, with extensive experience in assessment, diagnosis, and treatment of sleep disorders in populations including individuals with comorbid medical, psychological, and addictive disorders ([name], 1996; [name] et al., 2013; [name] et al., 2014). [name] research demonstrated the value of CBT-I in improving both chronic pain and sleep among a comorbid older adult sample, whereas pain treatment alone did not result in long-term improvements in sleep ([name] et al., 2013; [name] et al., 2014). [name] expertise in sleep assessments, CBT-I and RCTs, while historically focused on older adults, will integrate well into the rest of the research team's expertise in AOD interventions for YA. [name] has similarly demonstrated feasibility and initial efficacy of CBT-I among college students with primary insomnia, demonstrating moderate-to-large effect sizes on a broad range of sleep outcomes ([name] et al. 2014).

5). Pilot data on YA sleep problems, comorbid alcohol and MJ use, and CBT-I for sleep and MJ use. The Transitions project (R01AA022087; [name] PI, [name] Co-I) included items on sleep and alcohol and MJ use in a diverse sample of 644 YA. Among YA who used alcohol in the past month, 59% scored 5+ on the PQSI, indicative of sleep dysfunction. Alcohol-related consequences from the Brief YAACQ were correlated with Global PQSI score as well as Daytime Dysfunction, Sleep Aid, Sleep Latency, and Sleep Disturbance subscales. Peak BAC, total weekly drinks, average drinks per day, and frequency of drinking were also correlated with the Sleep Aid subscale; 12% reported using alcohol as a sleep aid in the past month. Similarly, among those who used MJ at least monthly, 63.9% reported PQSI global scores above 5. Global PQSI and all subscales were correlated with MJ frequency. [name] also has expertise in bidirectional associations between sleep and MJ among YA Veterans, directly relevant to our hypotheses. Poor sleep quality among

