General Design: Baseline, Daily Monitoring, and Longitudinal Follow-Up Assessments. Participants who meet criteria will immediately be linked to the baseline survey online. Upon completion of baseline, they will be automatically randomized (programmed in DatStat Illume) to one of the 3 conditions using urn randomization (Wei & Lachin, 1988) to reduce disparities in baseline alcohol use and consequences, MJ use, and severity of sleep problems across conditions. Participants will be immediately routed to an online scheduling system listing multiple dates to choose to attend one (AOC) or two (BASICS + SLEEP, BASICS) in-person meetings. The first will be at least 2 weeks from baseline to enable sufficient time for baseline daily monitoring. Upon scheduling, an immediate email reminder will be automatically generated, including a link to a map to assist with locating the scheduled session. Participants will also receive a reminder call and email and text message the day prior to their meeting. Missed meetings will be rescheduled. Participants in all conditions will also receive a link to online daily diaries the morning after baseline, and a text message reminding them to log in the next morning to begin their first 14-day monitoring period (see diary procedures). Participants in all conditions will complete 4 additional weeks of daily monitoring corresponding with timing of interventions.

Daily, post-, and follow-up assessments for AOC will be yoked for timing to intervention for BASICS and BASICS + SLEEP, so assessments of alcohol, MJ, and sleep diaries will be at comparable times across groups. Three-month follow-up will replicate the email, text, and telephone reminders (see retention below and in human subjects), and participants will complete 2 weeks of daily monitoring at follow-up (see Figure 1). All participants will complete satisfaction scales at post-assessment as well as measures of outcomes and potential mediators to inform the future longitudinal RCT. Repeated daily assessments allow us to closely model the natural history of changes in alcohol, MJ, and sleep across the 3-month period, adding to sparse literature on this topic.

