Research Evaluating Sleep & Trends for Universal Prevention (REST-UP)

NCT04783519

03/27/2024

Statistical Design and Power

Preliminary analysis. Prior to inferential statistics, univariate and bivariate descriptive statistics will be used to assess distributions and simple relations among variables. Preliminary analyses will include nature of missing data, identification of extreme values and variable distributions. To establish randomization effectiveness, baseline equivalence on drinking measures and demographic representation will be examined between conditions. Preliminary efficacy (Aim 1) will be evaluated with respect to drinking behavior (quantity/frequency/peak drinking, total drinks per week, alcohol consequences) and sleep symptoms (as measured by the ISI and Promis). Secondary outcomes include MJ use and consequences.

To examine intervention differences in outcomes from post-intervention through 3-month follow-up, multilevel regression analyses (Gelman & Hill, 2007) – often referred to as Hierarchical Linear Modeling (HLM; Raudenbush & Bryk, 2002) or mixed-effects modeling (Pinheiro & Bates, 2000) – will be used. HLM has a number of advantages over traditional analytic techniques, such as repeated measures ANOVA, in that it allows for missing data, handles varying time-points, accommodates both time-varying and time-invariant covariates, and allows for flexible modeling of the correlation among repeated-measures. In the proposed project, each participant will provide up to 2 repeated measures (post-intervention, 3 months), yielding up to 300 Level 1 cases (repeated-measures) across 150 Level 2 cases (people). The following model will be the basis for analyses of specific aims:

$$\text{Level 1: } DV_{ti} = \pi_{0i} + \pi_{1i}(Time)_{ti} + \varepsilon_{ti} \quad \varepsilon_{ti} \sim N(0, I\sigma^2_{\varepsilon}) \quad (\text{Equation 1})$$

$$\begin{aligned} \text{Level 2: } \pi_{0i} &= \beta_{00} + \beta_{01}(DV_{pre})_i + \beta_{02}(Tx)_i + r_{00i} \\ \pi_{1i} &= \beta_{10} + \beta_{11}(DV_{pre})_i + \beta_{12}(Tx)_i + r_{10i} \end{aligned}$$

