where t indexes repeated-measures and i indexes participants. DV_{ti} represents the outcome vector for each individual from post-intervention through 3-months. $Time_{ti}$ measures weeks since end of intervention. DV_{pre} is the pre-intervention value of the outcome. (Note that sometimes DV_{pre} is included as the first datum in the outcome vector; most biostatisticians now reserve the outcome in treatment studies for post-randomization data that can be influenced by the treatment, see Harrell, 2004). Tx represents contrasts (i.e., dummy codes) for treatment condition. The multilevel model fits subject-specific effects via the random-effects (rs in Level 2); these “shrinkage” (Empirical Bayes) estimators are weighted combinations of individual and group level information. The model assumes independence of Level 1 residuals conditional on random-effects, and homoskedasticity and (multivariate) normality of Level 1 residuals and Level 2 random-effects (Atkins, 2005). The model depicted above represents the primary model to test intervention differences in outcome. The necessity of terms in the model will be assessed via Wald statistics for fixed-effects and deviance tests for random-effects. Clinical trials of psychological outcomes assessed repeatedly often have a nonlinear trajectory, which is well-modeled by the natural logarithm of time. If there is a nonlinear trajectory that is not fit via the log transformation, polynomials or spline fits will be used to model the curvature. Alcohol and MJ outcomes are frequently positively skewed, calling into question the use of the Normal distribution as the probability model. Rate and frequency variables, such as number of alcohol problems, often have skewed distributions that are better represented by the Poisson or Negative Binomial distributions (Atkins et al., 2013; Atkins & Gallop, 2007). Depending on observed outcome distributions, a generalized mixed-effects model with log-link a Poisson distribution may be appropriate (Raudenbush & Bryk, 2002). This model is a type of HLM with a Poisson distributed Level 1 outcome, the only notable change to equation 1.

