Power. We used PASS software to estimate effect sizes based on proposed study sample size for Aim 1b. In Aim 1b, the models will be run such that there will be two repeated measures of the outcome at follow- up. Given 50 participants per condition, this means that there will be up to 200 observations for any one comparison of an intervention to the control group (2 conditions x 50 subjects per condition x 2 observations per subject). However, the effective sample size will be smaller than 200 due to the design effect for the correlation of observations within participants (Snijders & Bosker, 1999). Thus, we can use an effective sample size to estimate the effect of an intervention compared to control at any given follow-up visit. Given the sample size, 2 repeated observations, and an anticipated intra-class correlation (ICC) among survey responses for the same individual of .6, the effective sample size for any given comparison between two groups would be 125. Using this effective sample size and standardizing the sleep outcome with a mean of 0 and SD of 1, we would expect $>.8$ power to detect moderate-sized coefficients for the difference between intervention and control as small as .5. If the outcome were typical number of drinks per week, which tends to show a count distribution, and the base-rate were 4 drinks per week, then we expect $>.8$ power to detect a 32% increase in the count of drinks per week in the control compared to intervention group at any given follow-up (Rate Ratio = 1.32).

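### The sleep models (ISI, PROMIS) leave out the alcohol and marijuana baselines that the urn balances: a cheap precision gain, not an error

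*Protocol*

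**What the plan says.** The protocol (General Design) assigns participants by urn randomisation "to reduce disparities in baseline alcohol use and consequences, MJ use, and severity of sleep problems across conditions". That gives four balancing domains: alcohol use, alcohol consequences, marijuana use and sleep severity.

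The SAP (Preliminary analysis) evaluates preliminary efficacy on drinking outcomes and on "sleep symptoms (as measured by the ISI and Promis"). In Equation 1, the Level 2 equations for the intercept and for the slope each contain only treatment and one baseline term, defined thus: "DV_{pre} is the pre-intervention value of the outcome". The SAP adds: "The model depicted above represents the primary model to test intervention differences in outcome".

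Two other places could have brought the urn factors in, and neither does:

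- The protocol's Measures table labels other drug use, psychiatric symptoms, demographics and social desirability as covariates. None of these is an urn factor.
- The SAP says "The necessity of terms in the model will be assessed via Wald statistics for fixed-effects". This concerns terms already in the model and names no alcohol or marijuana baseline as a candidate.

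**The concern.** When a trial balances its allocation on baseline variables, the usual practice is to carry those variables into the analysis. If they are prognostic, balancing reduces the true variability of the treatment contrast, but an unadjusted model does not credit that reduction in its standard error. Here the sleep models carry baseline sleep and leave the alcohol and marijuana baselines in the residual.

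The protocol gives reason to think these baselines may matter for sleep. Its Significance section says "Research demonstrates bidirectional causal links between alcohol misuse and sleep difficulties". Its pilot data (Preliminary/Pilot Studies, item 5) report that "Global PQSI and all subscales were correlated with MJ frequency" and that alcohol consequences correlated with the global sleep score. Neither statement shows prediction beyond a participant's own baseline sleep score, so the size of any gain is open.

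What is at stake is slightly wider confidence intervals than necessary for ISI and PROMIS, in a pilot with 50 per arm, when the data to narrow them are collected before randomisation. Bias is not at stake.

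**Working it through.** **1. The plan's own figure.** The SAP's Power section takes two arms of 50, two visits and an "anticipated intra-class correlation (ICC) among survey responses for the same individual of .6". Effective sample size = 200 / (1 + (2 − 1) × 0.6) = 125, as stated. With 62.5 per group, SD 1 and a two-sided 5% level (assumed; the SAP does not state one), SE = √(2/62.5) = .179. Power at a .5 SD difference is .798 by the normal approximation and .792 by the t distribution, against the stated >.8. The effect detectable with 80% power is .501 SD. The figure reproduces, and omitting the urn factors does not affect it.

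**2. Closed form for the gain.** Let R² be the share of the variance left after the outcome's own baseline that the added covariates explain. The SE is multiplied by √(1 − R²): √.95 = .975 at 5% and √.90 = .949 at 10%, so 2.5% and 5.1% smaller. The cost of three covariates in a single-visit ANCOVA with n = 150 and four existing terms is √((150 − 4 − 1)/(150 − 4 − 3 − 1)) = √(145/142) = 1.0105. The net reduction is then 1 − .975 × 1.0105 = 1.5% at 5%, and 1 − .949 × 1.0105 = 4.1% at 10%. At R² = 0 there is a loss of about 1%.

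**3. Simulation of the planned two-visit model.** There were 10,000 null trials and 10,000 with a .5 SD effect per setting.

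- From the documents: N = 150, three arms, two visits, ICC .6.
- Assumed: correlation of .6 between baseline and follow-up; correlation of .3 among the four baseline factors; median splits for the urn; an urn that starts with one ball per arm, adds one ball for each other arm after an assignment, and draws from the most imbalanced urn; alcohol and marijuana measures as rounded lognormal counts (log SD .8), entered as log(x+1).
- Model: random intercept, with intercept and slope each on treatment and own baseline; urn covariates in the intercept only. The random slope is left out because two repeats cannot separate it from the residual.

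Results for the post-intervention contrast, planned / adjusted, where change = planned/adjusted − 1 (the rounded entries reproduce each change to within 0.1 point):

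| Extra R² | Reported SE | Change | Sampling SD | Change | Power at .5 SD |
|---|---|---|---|---|---|
| 0 | .1607 / .1617 | −0.6% | .1605 / .1614 | −0.6% | .869 / .866 |
| 2% | .1606 / .1600 | +0.4% | .1607 / .1603 | +0.2% | .870 / .874 |
| 5% | .1606 / .1576 | +1.9% | .1603 / .1578 | +1.6% | .874 / .883 |
| 10% | .1608 / .1535 | +4.7% | .1588 / .1538 | +3.2% | .875 / .900 |

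Linear interpolation between the first two rows puts break-even at .6/(.6 + .4) × 2% = 1.2% for the reported SE and .6/(.6 + .2) × 2% = 1.5% for the sampling SD. Type I error lies between .045 and .054 for both models (Monte Carlo error .002). An independently coded repeat gave SE changes of −0.6, +0.4, +2.0 and +4.7%.

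Simulated power is above the SAP's because the model credits baseline sleep: √(.64 × 2/50) = .160, against .179 in step 1.

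**4. Sensitivity of the SE change (R² 0 / 2 / 5 / 10%).**

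- Prognosis follows the raw skewed counts but logs are entered: −0.6 / +0.2 / +1.5 / +3.7%.
- Baseline-to-follow-up correlation .4: −0.7 / +0.3 / +1.9 / +4.7%.
- Median-split codes instead of continuous measures: −0.5 / +0.2 / +1.3 / +3.2%.
- 15% or 20% missing at 3 months: −0.6% at R² 0, +1.9% at 5%, +4.7 to +4.8% at 10%.

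**5. Is the R² range plausible?** With total variance 1, ICC .6 and baseline correlation .6, baseline explains .36 and leaves .64. Of that, .60 − .36 = .24 is stable between persons. An extra R² of 2, 5 or 10% needs .02, .05 or .10 × .64/.24 = 5, 13 or 27% of that stable part. A value of 20% would need 53% and was not used.

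**6. Count outcomes.** In a Poisson model with a person-level random intercept (1,500 trials), sampling SD changed by −0.8 / −0.1 / +1.0 / +4.1% at R² 0 / 5 / 10 / 20%, and adjusted type I error reached .064. There is no useful gain, so drinking and consequence outcomes are outside this point.

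**The case against.** The strongest reply is that nothing is broken: the test is valid, planned power is already about .87 at .5 SD in the simulation, and adjustment moves it by only −.003 to +.025. That stands, and it sets the priority of the point.

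Second, the driving quantity has no source. The pilot correlations are of unstated size, use a different sleep index and are not adjusted for baseline sleep. For alcohol use itself, the pilot reports a link only with the sleep-aid subscale. Eligibility also requires recent heavy drinking and monthly marijuana use, which may restrict range and weaken any association. This stands too, and is why the range starts at zero.

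Third, the sampling SD, which is the actual precision, gains less than the reported SE: 3.2% against 4.7% at R² 10%. Part of the benefit has already been delivered by the urn. This is correct, so both columns are shown.

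Fourth, if the covariates in the Measures table were also entered, the increment from alcohol and marijuana could shrink. That is possible, but Equation 1 includes none of them and the simulation follows Equation 1.

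These replies limit the size of the gain. None puts the urn factors into the sleep models or shows a material cost of doing so.

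**Conclusion.** The point holds as a low-stakes improvement. For ISI and PROMIS, the primary model omits the alcohol and marijuana factors by which the trial balances its randomisation. If they explain 5–10% of the variance left after the outcome's own baseline, the reported SE is about 2–5% larger than it needs to be and the sampling SD about 1.6–3.2% larger. If they explain nothing, adjusting costs about 0.6%; the gain starts at roughly 1.2–1.5%. This rests on an assumed R², an assumed urn scheme and assumed correlations, since the documents give none of these. The case of four added covariates for PROMIS was not simulated separately. The trial's conclusions are valid without the change.

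**What to change.** In the SAP, for the normally modelled Aim 1b sleep outcomes:

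- Pre-specify one baseline measure for each remaining urn domain, using the variable that the randomisation program uses for alcohol use, alcohol consequences and marijuana use. Add the sleep-severity variable when it is not the same measure as the outcome's own baseline. Name each variable.
- Enter each in continuous form where available, with skewed alcohol and marijuana measures as log(x+1), as a fixed Level 2 intercept covariate without a Time interaction.
- Keep the outcome's own baseline, and do not enter the same measure twice.
- Exempt these terms from the Wald check, so that they are not selected on the data.

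For count-modelled drinking and consequence outcomes, keep the planned model as primary and report the adjusted model, with overdispersion handled, as a sensitivity analysis only. If sleep outcomes have already been analysed by arm, label the adjusted sleep model a sensitivity analysis as well.

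The cost is SAP wording and three covariates for ISI, three or four for PROMIS, all from measures planned before randomisation. The downside is three or four degrees of freedom, and an SE about 0.6% wider (about 1% in a single-visit ANCOVA) if the factors turn out not to be prognostic.

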Research Evaluating Sleep & Trends for Universal Prevention (REST-UP)

NCT04783519

03/27/2024

Statistical Design and Power

Preliminary analysis. Prior to inferential statistics, univariate and bivariate descriptive statistics will be used to assess distributions and simple relations among variables. Preliminary analyses will include nature of missing data, identification of extreme values and variable distributions. To establish randomization effectiveness, baseline equivalence on drinking measures and demographic representation will be examined between conditions. Preliminary efficacy (Aim 1) will be evaluated with respect to drinking behavior (quantity/frequency/peak drinking, total drinks per week, alcohol consequences) and sleep symptoms (as measured by the ISI and Promis). Secondary outcomes include MJ use and consequences.

To examine intervention differences in outcomes from post-intervention through 3-month follow-up, multilevel regression analyses (Gelman & Hill, 2007) – often referred to as Hierarchical Linear Modeling (HLM; Raudenbush & Bryk, 2002) or mixed-effects modeling (Pinheiro & Bates, 2000) – will be used. HLM has a number of advantages over traditional analytic techniques, such as repeated measures ANOVA, in that it allows for missing data, handles varying time-points, accommodates both time-varying and time-invariant covariates, and allows for flexible modeling of the correlation among repeated-measures. In the proposed project, each participant will provide up to 2 repeated measures (post-intervention, 3 months), yielding up to 300 Level 1 cases (repeated-measures) across 150 Level 2 cases (people). The following model will be the basis for analyses of specific aims:

$$\text{Level 1: } DV_{ti} = \pi_{0i} + \pi_{1i}(Time)_{ti} + \varepsilon_{ti} \quad \varepsilon_{ti} \sim N(0, I\sigma^2_{\varepsilon}) \quad (\text{Equation 1})$$

$$\begin{aligned} \text{Level 2: } \pi_{0i} &= \beta_{00} + \beta_{01}(DV_{pre})_i + \beta_{02}(Tx)_i + r_{00i} \\ \pi_{1i} &= \beta_{10} + \beta_{11}(DV_{pre})_i + \beta_{12}(Tx)_i + r_{10i} \end{aligned}$$

where t indexes repeated-measures and i indexes participants. DV_{ti} represents the outcome vector for each individual from post-intervention through 3-months. $Time_{ti}$ measures weeks since end of intervention. DV_{pre} is the pre-intervention value of the outcome. (Note that sometimes DV_{pre} is included as the first datum in the outcome vector; most biostatisticians now reserve the outcome in treatment studies for post-randomization data that can be influenced by the treatment, see Harrell, 2004). Tx represents contrasts (i.e., dummy codes) for treatment condition. The multilevel model fits subject-specific effects via the random-effects (rs in Level 2); these “shrinkage” (Empirical Bayes) estimators are weighted combinations of individual and group level information. The model assumes independence of Level 1 residuals conditional on random-effects, and homoskedasticity and (multivariate) normality of Level 1 residuals and Level 2 random-effects (Atkins, 2005). The model depicted above represents the primary model to test intervention differences in outcome. The necessity of terms in the model will be assessed via Wald statistics for fixed-effects and deviance tests for random-effects. Clinical trials of psychological outcomes assessed repeatedly often have a nonlinear trajectory, which is well-modeled by the natural logarithm of time. If there is a nonlinear trajectory that is not fit via the log transformation, polynomials or spline fits will be used to model the curvature. Alcohol and MJ outcomes are frequently positively skewed, calling into question the use of the Normal distribution as the probability model. Rate and frequency variables, such as number of alcohol problems, often have skewed distributions that are better represented by the Poisson or Negative Binomial distributions (Atkins et al., 2013; Atkins & Gallop, 2007). Depending on observed outcome distributions, a generalized mixed-effects model with log-link a Poisson distribution may be appropriate (Raudenbush & Bryk, 2002). This model is a type of HLM with a Poisson distributed Level 1 outcome, the only notable change to equation 1.

Aim 1b: Preliminary Treatment Outcome. The primary comparison is post-intervention differences between the BASICS + SLEEP vs. AOC and BASICS vs. AOC. The coding for Tx will depend on which hypothesis is being tested. Coefficients representing the main effect of treatment (i.e., “intercept” differences at post- intervention) and cross-level interactions of treatment contrast and Time will be used to test H1b. These two sets of coefficients will show whether there are treatment differences at the end of therapy and also across the 3-months post-therapy. As noted, appropriate Level 1 distribution (i.e., Normal or Poisson) will be used, determined by empirical distribution of outcomes. Secondary analyses will examine MJ using these approaches. We anticipate small-to-moderate effect sizes for alcohol and MJ use and moderate-to-large effects on sleep symptoms; recent trials have demonstrated large pre-post effects on alcohol and sleep indices for an integrated intervention with college students (Fucito et al., 2017).

Missing data. Multilevel models can incorporate missing data; however, validity of the findings depends on the missingness mechanism (see Atkins, 2005). There are 3 common assumptions for missing data (Schafer & Graham, 2002), and multilevel models provide unbiased results unless data are found to be non-ignorable (NI). HLM is generally resilient to missing data because HLM weights each person's final within-person slope and intercept estimates by the reliability of these estimates, which is influenced by the relative variance components and the number of observations that person provides. Data from individuals with fewer assessment points have less influence on the final results. More problematic is NI data, which arises when missingness depends on unobserved values of the outcome or upon a covariate not included in the model. In the present study, participants could fail to provide data due to alcohol use, which would yield NI missing data. This would only lead to NI data if the missingness were not related to earlier values of the DV.

To deal with this possibility, we will use both design and statistical controls. First, as noted in Approach and Recruitment and Retention Plan in the Human Subjects and Clinical Trials section, we make every attempt to retain all participants at all assessments, and HLM models include all participants in all analyses even if missing data at some assessment points and/or on some items. Second, handling NI missing data is an active area of statistical research, and there are several options that attempt to provide unbiased estimates in the presence of NI missing data, including selection models, pattern-mixture models, and shared parameter models (Schafer & Graham, 2002). We will use the pattern-mixture approach to missing data that has been extended to HLM (Hedeker & Gibbons, 1997) to examine the sensitivity of our primary findings to key patterns of missing data. Should these sensitivity analyses reveal that the findings are dependent on missing data, the pattern-mixture approach will allow us to combine effects across missing data patterns to yield unbiased treatment results (see Hedeker & Gibbons, 1997 and Atkins, 2005 for examples).

Power. We used PASS software to estimate effect sizes based on proposed study sample size for Aim 1b. In Aim 1b, the models will be run such that there will be two repeated measures of the outcome at follow- up. Given 50 participants per condition, this means that there will be up to 200 observations for any one comparison of an intervention to the control group (2 conditions x 50 subjects per condition x 2 observations per subject). However, the effective sample size will be smaller than 200 due to the design effect for the correlation of observations within participants (Snijders & Bosker, 1999). Thus, we can use an effective sample size to estimate the effect of an intervention compared to control at any given follow-up visit. Given the sample size, 2 repeated observations, and an anticipated intra-class correlation (ICC) among survey responses for the same individual of .6, the effective sample size for any given comparison between two groups would be 125. Using this effective sample size and standardizing the sleep outcome with a mean of 0 and SD of 1, we would expect $>.8$ power to detect moderate-sized coefficients for the difference between intervention and control as small as .5. If the outcome were typical number of drinks per week, which tends to show a count distribution, and the base-rate were 4 drinks per week, then we expect $>.8$ power to detect a 32% increase in the count of drinks per week in the control compared to intervention group at any given follow-up (Rate Ratio = 1.32).

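### H1b claims benefit over AOC at 3 months, but neither coefficient that Aim 1b tests is a test or confidence interval for the 3-month difference

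*SAP*

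**What the plan says.** **Hypothesis.** H1b (Protocol, Specific Aims) says that both active arms will do better than AOC on alcohol outcomes and sleep at two times: post-intervention and 3 months.

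**Model.** Equation 1 in the SAP has two outcome visits, adjusts for the baseline value, and lets treatment enter the intercept (b02) and the slope on Time (b12). Time "measures weeks since end of intervention".

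**Tests.** SAP Aim 1b sets the priority: "The primary comparison is post-intervention differences between the BASICS + SLEEP vs. AOC and BASICS vs. AOC". It describes the treatment main effect as the intercept difference at post-intervention and adds that "cross-level interactions of treatment contrast and Time will be used to test H1b". It then says: "These two sets of coefficients will show whether there are treatment differences at the end of therapy and also across the 3-months post-therapy".

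**Power.** The SAP's Power section uses an effective sample size to "estimate the effect of an intervention compared to control at any given follow-up visit". Visit-specific effects are therefore intended, but that section does not define the contrast that delivers them.

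**The concern.** Because Time starts at the end of the intervention, Tx is the difference at that point and Tx x Time is how fast the difference changes afterwards. A test of change answers a different question from a test of whether a difference exists at 3 months. A benefit that is fully maintained puts Tx x Time at its null value. A benefit that disappears makes Tx x Time likely to be significant. So the second named test cannot support or refute the 3-month half of H1b, and the first concerns the other visit.

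At stake is how the 3-month result will be reported. With no contrast fixed in advance, one analyst might evaluate the model at 3 months, another might read a non-significant interaction as a maintained benefit, and another might average the two visits. These can disagree.

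**Working it through.** **Inputs.** From the SAP's Power section: 50 per arm, two visits, SD 1, ICC .6, effect .5. Assumed here: two-sided 5% (the SAP states no alpha), complete normal data and, for adjusted figures, a correlation of .6 between baseline and each follow-up. Unadjusted figures are in square brackets.

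**1. The plan's own figure.** Effective N = 200 / (1 + (2 - 1) x .6) = 125, as stated. With 62.5 per arm, SE = sqrt(2/62.5) = .179. Then .5/.179 = 2.795, and 2.795 - 1.96 = .835, which gives power .798. This matches the plan's .8 to rounding.

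**2. What the coefficients are.** Substituting Level 2 into Level 1, the difference from AOC at time t is b02 + t*b12.

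| Quantity | Expression | Named for H1b in Aim 1b? |
|---|---|---|
| Difference at post-intervention | b02 | Yes |
| Change in the difference by 3 months | T*b12 | Yes (test of b12) |
| Difference at 3 months | b02 + T*b12 | No |

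Here T is the Time value at the 3-month visit. The variance of the last row is Var(b02) + T^2*Var(b12) + 2T*Cov(b02, b12), so two separate coefficient tests do not supply it. Unadjusted it is .040 + .032 - .032 = .040. Leaving out the covariance would give .072.

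**3. Standard errors.**
- One visit: sqrt(2 x .64/50) = .160 adjusted, where .64 = 1 - .6^2; [sqrt(2/50) = .200].
- Change between visits: sqrt(2 x .8/50) = .179 either way. The adjusted variance is 2 x (.64 - .24) = .8, with residual covariance .24 = .6 - .36. The unadjusted variance is 2 x (1 - .6) = .8.
- Mean of the two visits: sqrt(2 x .44/50) = .133, where .44 = (.64 + .24)/2; [sqrt(2 x .8/50) = .179].

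**4. Chance of a significant result, unadjusted, normal approximation.**

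| True effect: post / 3 months | Tx | Tx x Time | Direct 3-month contrast |
|---|---|---|---|
| .5 / .5 | .705 | .05 | .705 |
| .5 / .25 | .705 | .287 | .240 |
| .5 / 0 | .705 | .798 | .05 |
| 0 / .5 | .05 | .798 | .705 |

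The Tx x Time column does not follow the 3-month effect: it is .05 when the whole benefit is there and .798 when none is. Simulation (40,000 replicates, three arms of 50) gives 79% for the latter, adjusted or not. With adjustment the direct contrast at .5 rises to 87%.

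**5. If 'Tx significant, Tx x Time not' were read as benefit at 3 months (simulation).**
- Benefit .5 then nil: the pattern occurs in 14% [10%]; a direct test of benefit gives 2.5%. With baseline correlation .4 or .7, the 14% becomes 11% or 16%.
- Benefit .5 maintained: pattern 84% [67%], direct contrast 87% [70%].
- Benefit growing from .25 to .5: the pattern or a favourable Tx x Time occurs in 59% [50%], direct contrast 87% [70%].

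**The case against.** The strongest reply is that nothing essential is missing. The model yields the 3-month difference, Aim 1b uses both coefficient sets together, and the Power section speaks of effects at each follow-up. On that view only a line of notation is absent, and in a pilot of preliminary efficacy that is minor. Much of this stands: no new model or data are needed. But H1b names 3 months explicitly, and the tests named for it do not test that difference.

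Several stronger readings are tempting and are not supported.

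- **That 14% is the plan's error rate.** The SAP nowhere says that a non-significant interaction will be taken as maintained benefit. The figure is conditional on that reading and on complete loss of a .5 SD effect. The protocol gives no reason to expect such a loss and cites BASICS effects lasting up to 4 years. With partial decay (.5 to .25) a 3-month benefit does exist; the pattern then occurs in 60% [45%] of trials, against about 35% [24%] for the direct contrast (.25/.160 = 1.56, 1.56 - 1.96 = -.40; [.25/.200 = 1.25, 1.25 - 1.96 = -.71]). That reading then reaches the right qualitative answer more often, although it remains no test of the 3-month difference.
- **That Tx x Time will be dropped.** The SAP says "The necessity of terms in the model will be assessed via Wald statistics for fixed-effects", but it does not say that a non-significant interaction is removed. Aim 1b needs that interaction for H1b, so removing it would conflict with the plan.
- **That log time breaks the analysis.** The SAP describes a common non-linear trajectory "which is well-modeled by the natural logarithm of time". The log is undefined at week 0, so the zero point needs stating if it is used. But with visit times varied (assumed post 0 to 1 week, follow-up 11 to 16 weeks), linear and ln(Time + 1) both gave the pattern in 16% of lost-benefit trials, so no added harm was shown.
- **That the two active arms cannot be compared directly.** Aim 1b lets the Tx coding vary with the hypothesis, so that contrast is available.

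**Conclusion.** The point holds for the 3-month half of H1b and should be fixed. Aim 1b tests the post-intervention difference and its change, and names no test or interval for the 3-month difference that H1b claims. The gap is one of specification, since the planned model already contains the quantity.

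Its size is shown by Tx x Time being significant in 5% of trials when a .5 SD benefit is maintained and in about 79% when it is lost. That contrast uses the SAP's sample size, SD and ICC, with an assumed two-sided 5% level and complete normal data. It does not depend on the assumed baseline correlation; the adjusted power figures and the 14% do.

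A reader might infer that the trial's main efficacy test is compromised. It is not: the post-intervention comparison with AOC is primary, and b02 tests it correctly with the interaction retained and Time linear.

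**What to change.** State in Aim 1b that:

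- from the baseline-adjusted three-arm model, with Tx x Time retained, each active arm minus AOC will be estimated with a 95% CI at post-intervention (primary) and at the 3-month visit;
- each estimate is the Tx coefficient plus every Tx-by-time term evaluated at that visit's time under the time function used (b02 + T*b12 if linear), with its variance taken from the full covariance matrix and exponentiated to a rate ratio for count outcomes;
- Tx x Time is reported only as a test of change between visits.

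The cost is a few sentences and contrast statements, with no new data or model. The downside is power: if a .5 SD benefit is maintained, a visit-specific test has 87% [70%], against 96% [79%] for an effect pooled over both visits.
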